### Appendix 3: Quantitative data collection tools

Appendix three includes the questions that will be asked to the participants who will be recruited in the quantitative cohort.

***Please note: these questionnaires are presented to inform readers of the wording of the questions. The response options, order and skip patterns are subject to change once programmed on electronic data capture devices.***

**“Exit” Interview Quantitative Cohort Questionnaire (Questions to be asked at the time of distribution – whether at ANC or ART)**

Section 0: Preparing for the survey			
Variable Name	Question	Options	Option Codes
PS 1	What is the date today?	[time stamp]	
PS 1a	CLINIC NAME	[EDC CODE]	
PS 2	Scan participant barcode		
PS 3	Which community are you in?	Community 1	1
		Community 2	2
		Community 3	3
		Community 4	4
		Community 5	5
		Other	Specify
PS 4	What models of HIV self-testing distribution are in this community? [tick all that applies]	VMMC	1
		Community- or facility led	2
		Secondary distribution through ANC	3
		Secondary distribution HIV testing and treatment services	4
		Workplace	5

		Other (Specify)	6
PS 5	Through which distribution model was the client offered an HIV self-testing kit?	Secondary distribution through ANC	3
		Secondary distribution through HIV testing and treatment services (ART and VCT)	4
Section 1: Consenting Process			
Consent 1	I would like to take some time to explain the research that we are carrying out in this study about HIV self-testing.  At the end of my explanation, you can decide whether you would like to participate and continue with answering specific questions for the study. Before we begin, do you have any questions?		
Consent 2	Obtain consent using the consent form written in the language that the participant understands		
Consent 3	DID THE INDIVIDUAL GIVE CONSENT TO PARTICIPATE IN THE STUDY?	No	0
		Yes	1
Section 2: Demographics			
	Today's date	Auto complete by EDC	
Demo 1	Sex	Male; Female	1;2
Demo 2	What is your date of birth?	DDMMYYYY	01011900 if unknown
Demo 4	How long have you been living in [NAME OF CURRENT PLACE OF RESIDENCE]?	Years: months	

Demo 5	How many minutes did it take you to come to the health facility?	TIME (minutes)	
Demo 6	What form of transport did you use?	Came on foot	
		Taxi	
		Private car	
		Bus	
		Bicycle	
		Other	
Demo 7	What is the highest level of education you have completed?	No education; Grade 1;Grade 2;Grade 3;Grade 4;Grade 5;Grade 6;Grade 7;Grade 8 Grade 9 ;Grade 10 ;Grade 11 ;Grade 12;College;University; Don't know/Refuse	0;1;2;3;4;5;6;7 ;8;9;11;12;13;-1

Demo 8	How can you best describe your main income generating activity or work status?	Farmer (own land); Farm work on employers land; Domestic; Work in bar, hotel, guest house; Fishing; Mining; Working in shop; Informal Selling; Commercial sex work; Transport (trucker, taxi driver); Factory; Guard (security company); Police/soldier; Clerical and office work; Government; Teacher; health care; Other Professional; Other (Specify)	
Demo 9	What is your religion?	Roman Catholic; Anglican; Seventh-Day Adventist; Baptist; Pentecostal; Salvation Army; Lutheran; Evangelical church; United Methodist/African Methodist; Jehovah's witness; New Apostolic church (NAC); Apostolic faith Mission (AFM); Zion Christian Church (ZCC); Other (Specify)	

Demo 10	What is your current marital status?	Single/never married; married/living together as if married; separated/divorced; widowed	1;2;3;4
Demo 11	Do you currently have a main/primary sexual partner?	No; Yes	0; 1
Demo 11a	How would you describe your relationship with this sexual partner?	Husband/wife (married or living as married); Boyfriend/girlfriend ; casual partner; One-time partner	1; 2; 3; 4
Demo 12	[FOR RA ONLY – WHAT IS THE PURPOSE OF THE VISIT TODAY?]	ANC; HIV testing and treatment services	1; 2
Demo 13	Did you come alone to the facility or you came with your partner	Alone; With my partner	1; 2
Section 3: History of attendance to ANC and of HIV testing			
H_ANC 1	Is this your first pregnancy?	No; Yes; Refuse to answer	0;1; -1
H_ANC 2	When was your last pregnancy or birth?	Year: month	
H_ANC 3	Did you attend antenatal care during your last pregnancy?	No; Yes	0; 1
H_ANC 4	During your last pregnancy, were you tested for HIV during?	No; Yes	0; 1
H_ANC 5	During your last pregnancy, was your partner also tested for HIV?	No; Yes NA (no partner at that time); Refuse to respond	0; 1;2; -1

H_ANC 6	When your partner was tested during your last pregnancy, where was the HIV test done?	ANC clinic I attended Mobile HTC VMMC Home-based He self-tested	1;2;3
H_ANC 7	Is this your first visit to ANC for this current pregnancy?	No; Yes; 2 nd ; 3 rd ; 4 th ; Other (Specify)	0;1; 2; 3; 4
Section 3a: Individuals attending ART Care			
H_ART 1	When did you first test HIV positive?	MM YYYY	
H_ART 2	When did you start ART treatment?	MM: YYYY	
H_ART 4	Have you disclosed your HIV status to anyone?	No; Yes	0; 1
H_ART 5	To whom did you disclose your HIV status?	husband/wife; Boyfriend/girlfriend /partner; Family Member; Friend/neighbour/c olleague; Religious leader/; Health care; Other (Specify)	1; 2; 3; 4; 5

Section 4: History and current HIV testing (Questions for women attending ANC)			
H_HIVCT 1	Have you previously tested for HIV?	No; Yes; Don't know/Refused	0;1; -1
H_HIVCT 2	How many times have you tested for HIV?		
H_HIVCT 3	Have you ever HIV tested using an HIV self-test?	No: Yes	0; 1

H_HIVCT 4	When did you last test for HIV?	DD:MM: YYYY	01011900 if date not known
H_HIVCT 5	What was the result of your last (most recent) HIV test?	Negative; Positive; Didn't receive; Don't know/Refused	0;1;2; -1
H_HIVCT 6	During this visit to the clinic, was HIV testing discussed with you?	No; Yes	0;1
H_HIVCT 7	During this visit to the clinic, was oral HIV self-testing discussed with you?	No; Yes	0;1
H_HIVCT 8	During this visit to the clinic, were you offered to self-test using an HIVST kit?	No; Yes	0; 1
H_HIVCT 9	Did you choose to do an oral HIV self-test?	Yes; No; Client doesn't know	1;0; -1
H_HIVCT 10	Why did you choose an oral HIV self-test?	Doesn't like needles; Wants to test at home; Too busy now, test later; Try new way of testing; Wants to test with partner; Other; Client doesn't know/refused; CHiP didn't ask/record; Other (specify)	1;2;3;4;5;9; -1; -2
H_HIVCT 11	What is your partners' date of birth?	DDMMYYYY	01019999 if unknown
H_HIVCT 12	If date of birth unknown, how old is your partner?		
H_HIVCT 13	Where does your partner live?	Same house; same community; outside community; Don't know	1; 2; 3; 4
H_HIVCT 14	How long has your partner been living in [NAME OF CURRENT		

	PLACE OF RESIDENCE]?		
H_HIVCT 15	What is the highest level of education your partner has completed?	No education; Grade 1; Grade 2; Grade 3; Grade 4; Grade 5; Grade 6; Grade 7; Grade 8; Grade 9; Grade 10; Grade 11; Grade 12; College; University; Don't know/Refuse	
H_HIVCT 16	How can you best describe your partner's main income generating activity or work status?	Farmer (own land); Farm work on employer's land; Domestic; Work in bar, hotel, guest house; Fishing; Mining; Working in shop; Informal Selling; Transport (trucker, taxi driver); Factory; Guard (security company); Police/soldier; Clerical and office work; Government; Teacher; health care; Other Professional; Other (Specify)	
H_HIVCT 17	How do you rate your partner's general health?	Very good; good; fair; poor; very poor	1;2;3;4;5
H_HIVCT 18	On average how many nights a week does your partner spend away from home for work, if at all?	0 (no nights away from home), 1, 2, 3, 4, 5, 6, 7	
H_HIVCT 19	Have you ever discussed HIV testing with your partner?	No; Yes	0; 1
H_HIVCT 20	Has your partner ever had an HIV test?	No; Yes; Don't know	0; 1; 2
H_HIVCT 21	When was the last time that your partner tested for HIV?	Year; month	

H_HIVCT 22	Do you know the result of your current partner's most recent HIV test?	No; Yes	0; 1
H_HIVCT 23	What is the HIV status of your partner?  INTERVIEWER: REMIND PARTICIPANT THAT THEY DO NOT HAVE TO ANSWER THIS QUESTION IF UNCOMFORTABLE. IF SHE SAYS THAT SHE KNOWS BUT DOESN'T WANT TO SHARE – THIS IS CODE 3. IF THE PERSON TESTED BUT DID NOT SHARE THE RESULT WITH THEM SO THEY DON'T KNOW, THIS IS CODE -1	Positive; Negative; partner has not tested (unknown); Partner tested – I know the result but I don't wish to share Don't know; Partner tested – but I don't know the result	1; 2; 3; 4; -1
H_HIVCT 24	Were you offered an HIVST to give to your partner?	No; Yes	0; 1
H_HIVCT 25	Did you accept the offer of an HIVST for use by your partner?	No; Yes	0; 1
H_HIVCT 26	If no, why did you not accept the offer of an HIVST for your partner?	Need partner's permission to take HIVST; Partner recently HIV tested; Partner not interested in HIV testing	
H_HIVCT 27	Before the offer of an HIVST for your partner, had you ever heard of HIVST?		
H_HIVCT 28	Do you think your partner will be comfortable receiving the HIV self-test kit from you?	No; Yes; Don't know	0;1; -1
H_HIVCT 29	If No, why would your partner be un-comfortable to receive the test kit from you?		
Section 5: Question on Intimate Partner Violence			
QIPV 1	If you told your partner that you are visiting the health facility today. And one of the services you	No; Yes; Don't know	0;1; -1

	will receive will include HIV testing, would he react angrily or negatively?		
QIPV 2	In the past 12 months, has your partner		
QIPV 3	Threatened to hurt you, your children or someone close to you?	No; Yes; Don't know	0;1; -1
QIPV 4	Hit, slapped, kicked, pushed, shoved or otherwise physically hurt you?	No; Yes; Don't know	0;1; -1
QIPV 5	If yes, in the past 12 months how many times has this happened to you?	Once; Twice; Three times; Four times; or more times; I don't know	1;2;3;4;5; -1
QIPV 6	In the past 12 months, has you're your partner insulted you or made you feel bad about yourself?	No; Yes; Don't know	0;1; -1
QIPV 6a	If yes, in the past 12 months how many times has this happened to you?	Once; Twice; Three times; Four times; or more times; I don't know	1;2;3;4;5; -1
	If yes to any of the above questions, the lay counsellor should inform the possible social harms that may occur and establish if it is safe to give an individual a test kit their partner.		
Section 6: Questions on gender norms			
QSN 0	Please indicate how strongly you agree or disagree with the following statements.		
QSN 1	"It is normal for a woman to start the discussion with the partner on HIV testing"	Strongly agree; agree; disagree; Strongly disagree	1;2;3;4
QSN 2	It is normal for a woman to ask her male partner to go for HIV testing: agree, disagree	Strongly agree; agree; disagree; Strongly disagree	1;2;3;4
QSN 3	"It is normal for the partner/husband to beat or insult	Strongly agree; agree;	1;2;3;4

	the wife if she has done something wrong. Such as giving him an HIV self-testing kit”	disagree; disagree	Strongly
Section 7: Screening Questions on Alcohol and Drug Use			
Alcohol_0	I will now ask you questions about drinking alcohol and drug use. I know these questions are sensitive and want to remind you that your answers are completely confidential. Do you have any questions before we begin?		
Alcohol_1	How often do you have a drink containing alcohol?	Never; Monthly or less; 2 to 4 times a month; 2 to 3 times a week; 4 or more times a week	1; 2; 3; 4; 5
Alcohol_2	How many drinks containing alcohol do you have on a typical day when you are drinking?	1 or 2; 3 or 4; 5 or 6; 7, 8, or 9; 10 or more	1; 2; 3; 4; 5
Alcohol_3	How often do you have six or more drinks on one occasion?	Never; Less than monthly; Monthly; Weekly; Daily or almost daily	1; 2; 3; 4; 5
Alcohol_4	How often during the last 12 months have you found that you were not able to stop drinking once you had started?	Never; Less than monthly; Monthly; Weekly; Daily or almost daily	1; 2; 3; 4; 5
Alcohol_5	How often during the last 12 months have you failed to do what was normally expected from you because of drinking?	Never; Less than monthly; Monthly; Weekly; Daily or almost daily	1; 2; 3; 4; 5
Alcohol_6	How often during the last 12 months have you needed a first drink in the morning to get yourself going after a heavy drinking session?	Never; Less than monthly; Monthly; Weekly; Daily or almost daily	1; 2; 3; 4; 5
Alcohol_7	How often during the last 12 months have you had a feeling of guilt or remorse after drinking?	Never; Less than monthly; Monthly; Weekly; Daily or almost daily	1; 2; 3; 4; 5
Alcohol_8	How often during the last 12 months have you been unable to	Never; Less than	1; 2; 3; 4; 5

	remember what happened the night before because you had been drinking?	monthly;      Monthly; Weekly;      Daily    or almost daily	
Alcohol_9	Have you or someone else been injured as a result of your drinking?	No; Yes, but not in the last year; Yes, during the last year	0; 1; 2
Alcohol_10	Has a relative or friend or a doctor or another health been concerned about your drinking or suggested you cut down?	No; Yes, but not in the last year; Yes, during the last year	0; 1; 2
Alcohol_11	Among people of similar age and sex as you in this community during an average month, how common do you think it is for them to have six or more drinks on one occasion?	Very common; somewhat common; somewhat uncommon; very uncommon	1; 2; 3; 4
Drugs_1	In your lifetime have you ever used any drugs recreationally?	No; Yes	0; 1
Drugs_2	In the last 12 months, have you used drugs recreationally?	No; Yes	0; 1
Drugs_3	In the last 12 months, which drugs have you used?	Cannabis/Marijuana; Cocaine/Crack; Khat/Miraa; Ecstasy/Disco biscuit; Heroin; Amphetamine/Speed; Tik; Nyamba (any drug mixed with ART and smoked); Glue/solvents/petrol sniffing;      Other (Specify)	1; 2; 3; 4; 5; 6; 7

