### **5.4 Sample size justification for secondary distribution cohorts (quantitative data collection)**

The primary aim of secondary distribution is to increase uptake of HIV testing services among the intended users. Through the secondary distribution cohorts, we will investigate factors associated with use of an HIVST as reported by the index individual. To meet this aim, our sample size is based on two key factors considered *a priori* to influence reported use of the HIVST: knowledge of partners HIV status in the ANC cohort and HIV status disclosure in the cohort of individuals who know their HIV-positive status. There limited evidence of factors associated with use of a secondary distribution HIVST. However, in both groups, we anticipate that reported use of the HIVST will be approximately two-times higher among pregnant

women who state they know their partners HIV status and among HIV-positive individuals who have disclosed their HIV status to their partner.

In a cohort study among women attending ANC in Kenya, ~87% reported distributing the HIVST to their primary partner and that the partner used the HIVST [14]. This was in a clinical trial scenario and so using this figure and extrapolating to a more real life scenario, we hypothesise that in this study among individuals who accept an HIVST, ~60% of women in ANC who report knowing their partners HIV status and ~60% of individuals who report having disclosed their HIV-positive status to their partner will report that their partner used the HIVST at 1-month follow-up. To be conservative in our estimates, we have assumed that 40% of those not reporting these factors will report that their partner used the HIVST. Based on these estimates we require a sample size of approximately 300 per cohort (~600 total) to have at least 80% power to detect this association at the p=0.05-level.

We anticipate that up to 30% of individuals who accept the offer may be lost to follow-up. To account for this potential loss to follow-up, we will therefore recruit approximately 450 individuals per cohort (approximately 900 individuals total) to maintain at least 80% power to detect this association at the p=0.05-level.

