### **4. Secondary distribution:**

The secondary distribution will be conducted in public health facilities. There will be two ways of distribution: 1. Through ANC and PNC clinics; 2. through index testing in HIV testing and treatment services.

- **Through ANC clinics:** The women attending ANC and PNC who receive routine provider-based HIV testing as per prevention of mother-to-child-transmission (PMTCT) guidelines will be offered an option of obtaining an HIVST kit for secondary distribution to their partners at home. The aim is to increase the uptake of HIV testing among couples in pregnancy and postpartum period for prevention of mother-to-child-transmission and to increase HIV testing amongst males.
- **Through index testing through HIV+ individuals:** In this model, clients enrolled in ART clinics and clubs, and those attending other HIV testing and treatment services such as VCT will be offered to obtain HIVST kit for secondary distribution to their partners at home. The aim is to increase the uptake of HIV testing in relationships where one partner is a known HIV positive. This will allow those in sero-discordant partnerships to prioritize effective HIV prevention, such as the use of condoms, immediate antiretroviral therapy (ART), medication adherence by HIV-positive partners, and pre-exposure prophylaxis.

The distribution will be carried out by existing lay counsellors and HCWs that are providing the HTS to the women attending ANC and those providing HIV testing and treatment services. As in other models, all potential testers will obtain HIVST kits as well as

information brochures, and self-referral cards for linkage to post-test services. Information on how to conduct a self-test will also be available on phones and tablets for clients to obtain or view. There will be no formal remuneration of work done but non-monetary recognition will be given to highly performing facilities. The target audience is the male partners who may not have presented themselves at ANC with their female partners and the partners of HIV+ clients. There will be no individual tracking for linkage to care and treatment, but this will be established through PHIA and demographic health surveys.

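### The HIV-positive cohort is sized on disclosure to the partner, but the exit interview captures that only indirectly, and perhaps not for VCT clients

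*Protocol*

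**What the plan says.** Protocol section 5.4 bases the sample size on one factor per cohort. For the HIV-positive cohort the factor is "HIV status disclosure in the cohort of individuals who know their HIV-positive status", made specific in the effect assumption: "60% of individuals who report having disclosed their HIV-positive status to their partner will report that their partner used the HIVST at 1-month follow-up". For the comparison group, "we have assumed that 40% of those not reporting these factors will report that their partner used the HIVST". The target is about 300 evaluable per cohort, to "have at least 80% power to detect this association at the p=0.05-level", raised to about 450 recruited for up to 30% loss.

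The exposure comes from the exit interview in Appendix 3, block "Section 3a: Individuals attending ART Care". H_ART 4 asks "Have you disclosed your HIV status to anyone", answered no or yes. H_ART 5 asks to whom. Its first two options are a spouse and a boyfriend, girlfriend or partner; the others are family, friends or colleagues, religious leader, health care and other.

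The cohort is wider than ART attenders. Appendix 1 says of ART clients and others that "those attending other HIV testing and treatment services such as VCT will be offered to obtain HIVST kit". Item PS 5 of the exit interview uses one code for ART and VCT together, and section 4.3.2 lists newly diagnosed HIV among the factors to be measured.

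**The concern.** The sizing factor is disclosure to one particular person, the partner who is to use the kit, and no item asks about that person. H_ART 4 is too broad. H_ART 5 comes closer but has four weaknesses:

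- It has no time frame, so disclosure to a former spouse or earlier partner fits the same option as disclosure to the present one.
- It is not linked to the intended kit user. The primary outcome in 4.3.2 allows for more than one partner and more than one kit.
- It carries no multi-response instruction, unlike PS 4 and SHS_Fu_2a. If one answer is stored, someone who told both a sister and the husband may be recorded under the sister only.
- It lists seven options against five codes.

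In addition, the heading of the block, read literally, leaves out VCT clients.

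At stake is the factor comparison on which the cohort is sized. Non-differential misclassification shrinks the expected 20-point difference, and missing exposure reduces the number analysed. The gap is hard to repair at 1 month, because handing over the kit may itself prompt disclosure: SHS_Fu_2a lists having been able to tell the partner one's status as a possible benefit.

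**Working it through.** **1. The plan's own figure.** Inputs from 5.4: 0.60 and 0.40, alpha 0.05 (taken as two-sided; not stated), at least 80% power, about 300 evaluable. The share f that has disclosed to the partner is not stated, so no unique sample size follows. With n1 = Nf, n0 = N(1−f) and pooled proportion p:

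power = Φ[(P1 − P0 − 1.96·s0)/s1], where s0 = √{p(1−p)(1/n1 + 1/n0)} and s1 = √{P1(1−P1)/n1 + P0(1−P0)/n0}.

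At N = 300 and f = 0.5: s0 = 0.0577, s1 = 0.0566, and (0.20 − 0.1132)/0.0566 = 1.535, giving 93.8%. At f = 0.7 power is 89.4%; at f = 0.8 it is 80.0%. The claim of at least 80% therefore holds for f between 0.2 and 0.8.

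Loss to follow-up: 300/0.70 = 429, so 450 covers it and leaves 450 × 0.70 = 315. At N = 315, with exposure measured without error, power is 94.8%, 90.8% and 81.9% for f = 0.5, 0.7 and 0.8.

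**2. Misclassified exposure.** Let se and sp be the sensitivity and specificity of recorded against true disclosure to the kit recipient, with error unrelated to kit use. All values are assumptions. Then

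- recorded as disclosed: m = f·se + (1−f)(1−sp)
- P1 = [0.6·f·se + 0.4(1−f)(1−sp)]/m
- P0 = [0.6·f(1−se) + 0.4(1−f)·sp]/(1−m)

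Example with f = 0.5, se = 1, sp = 0.9: m = 0.55, P1 = (0.30 + 0.02)/0.55 = 0.582, P0 = 0.40, power 89.8%.

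Example with f = 0.7, se = 0.8, sp = 1: m = 0.56, P1 = 0.60, P0 = (0.084 + 0.120)/0.44 = 0.464, power 67.5%.

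Difference in points, then power, at N = 315:

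| Assumed error | f = 0.5 | f = 0.7 | f = 0.8 |
|---|---|---|---|
| None | 20.0; 94.8% | 20.0; 90.8% | 20.0; 81.9% |
| se 1.0, sp 0.9 (H_ART 5; a few told a different partner) | 18.2; 89.8% | 19.2; 86.2% | 19.5; 76.7% |
| se 0.9, sp 0.9 | 16.0; 81.4% | 15.0; 71.6% | 13.3; 55.0% |
| se 0.8, sp 1.0 (one answer stored; 20% of partner disclosures missed) | 16.7; 83.0% | 13.6; 67.5% | 11.1; 47.9% |
| se 1.0, sp 0.5 (H_ART 4 used alone) | 13.3; 53.6% | 16.5; 55.4% | 17.8; 47.9% |

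**3. Missing exposure.** If the block is skipped for VCT clients, those with no value drop out and the difference stays at 20 points. With 20% missing (N = 252) power is 89.3%, 83.5% and 72.8% for f = 0.5, 0.7 and 0.8. With 40% missing (N = 189) it is 79.0%, 71.8% and 60.2%. These figures hold f fixed. If VCT clients disclose less often, the non-disclosed group shrinks further, but the documents give no figure for that.

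**4. The ANC cohort for comparison.** Its sizing factor, knowledge of the partner's HIV status, is asked about the current partner (H_HIVCT 22). The HIV-positive cohort has no matching item.

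**The case against.** A reader might infer that the form fails to measure the exposure at all, that VCT clients will have no value, and that a null result could not be told from a measurement failure. The documents do not support this.

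- H_ART 5 names spouse and partner, and Demo 11 and 11a record whether there is a current main partner and of what type. For an index patient with one main partner, disclosure can largely be derived.
- The worst row of the table for half disclosed, H_ART 4 alone, requires the analyst to ignore H_ART 5. Nothing in the protocol says so, and 5.4 points to the partner.
- The absence of a tick-all instruction does not prove single choice. Drugs_3 plainly admits several answers without one, and also has more options than codes.
- Headings in this draft are not reliable routing rules. Section 4 of the exit interview is headed for women at ANC, yet it holds the only offer and acceptance items, which 5.2 needs in both cohorts.
- Appendix 3 states that response options, order and skip patterns may change on programming.
- The primary outcome is a proportion reporting partner use and does not depend on disclosure. Section 7.3 treats the factor analysis as exploratory.

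These points stand, and they limit the finding to what may happen. They do not remove it. The Appendix 3 caveat covers options, order and skips, and presents the forms as showing the wording of the questions. Programming can settle the codes, multi-response and routing, but it would not supply a partner-specific question that is absent. Matching to Demo 11a also leaves former partners, additional partners and a recipient other than the main partner unresolved.

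**Conclusion.** The point holds in a limited form. The factor on which the HIV-positive cohort is sized is only indirectly derivable from the exit interview. It may be misclassified for some participants and missing for VCT clients, depending on final coding and routing.

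The size cannot be fixed from the documents, which give no misclassification rate, VCT share or disclosed share. At N = 315 the loss is minor in the mild case (about 90% power with half disclosed and specificity 0.9) and serious, at about 50 to 70%, under several of the heavier assumptions. The sample has slack when about half have disclosed: sensitivity and specificity of 0.9 still leave 81.4%. It has little slack when about 80% have disclosed. Missing exposure costs numbers and does not in itself dilute the contrast. The pull toward zero assumes error unrelated to kit use.

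This is a change that should be made because it is cheap and the exposure cannot be cleanly rebuilt later. It does not invalidate the cohort or its primary outcome.

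**What to change.** 1. Add one no/yes item for every HIV-positive index patient, at ART and at VCT: *Before today, had you told the partner for whom this kit is offered that you are HIV-positive?* Name it in section 5.4 as the exposure.
2. Mark H_ART 5 as tick all that apply, with one code per option, and keep it as descriptive.
3. Retitle Section 3a so that it covers all HIV-positive index patients.

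The cost is one extra question and minor edits to the electronic form, made before recruitment. The sample size need not change.

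### In the exit questionnaire, the H_HIVCT 23 interviewer note gives the wrong code, and the Section 4 heading limits to ANC women the acceptance and partner items that both cohorts need

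*Protocol*

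**What the plan says.** Section 5.4 of the Protocol sizes the two secondary distribution cohorts on two factors: "knowledge of partners HIV status in the ANC cohort and HIV status disclosure in the cohort of individuals who know their HIV-positive status". It assumes that partner use is reported by 60% of those with the factor and 40% of those without.

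For ANC women, Appendix 3 asks about the partner's status in two consecutive items of the exit interview. H_HIVCT 22 is a No/Yes question: "Do you know the result of your current partner's most recent HIV test". H_HIVCT 23 then asks what the status is. Its options begin "Positive; Negative; partner has not tested (unknown" and its codes are 1, 2, 3, 4 and -1. The third and fourth options read "partner has not tested (unknown); Partner tested – I know the result but I don't wish to share". The interviewer note inside the item says "IF SHE SAYS THAT SHE KNOWS BUT DOESN'T WANT TO SHARE – THIS IS CODE 3" and then "IF THE PERSON TESTED BUT DID NOT SHARE THE RESULT WITH THEM SO THEY DON'T KNOW, THIS IS CODE -1".

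The block that holds these items is headed "Section 4: History and current HIV testing (Questions for women attending ANC". It also holds the acceptance item, H_HIVCT 25: "Did you accept the offer of an HIVST for use by your partner".

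**The concern.** There are two separate faults in the form.

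**The code.** The note sends women who know the result but keep it private to the code for partners who have not been tested. An interviewer who follows it records a false partner status. Knowledge of that status is the factor on which the ANC cohort is sized, so the error could reach the main comparison, depending on which item defines the exposure. The Protocol does not name that item.

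**The heading.** Read literally, HIV-positive clients are not asked H_HIVCT 1 to 29. They would then not be asked whether they accepted the partner kit. That answer is secondary outcome 1 in section 4.3.2, the subject of objective 9, and the condition for follow-up. Nor would they be asked the partner's age, residence, education, work or testing history.

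**Working it through.** **1. Options against codes in H_HIVCT 23**

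| Code, by position | Option (paraphrased) | What the note says |
|---|---|---|
| 1 | partner positive | nothing |
| 2 | partner negative | nothing |
| 3 | partner not tested, status unknown | used for a woman who knows but declines to say |
| 4 | partner tested, she knows, declines to say | nothing |
| -1 | partner tested, she does not know | agrees with the list |

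The first four options and codes run in the same order. The note's other rule (-1) agrees with the list. So the mismatch is a wrong digit in the note and not an effect of a broken table.

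**2. The plan's own sample size**

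Inputs from section 5.4: 60% versus 40%, 80% power, 0.05 level (taken as two-sided), 30% loss. With equal groups,

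n = [1.96·√(2·0.5·0.5) + 0.842·√(0.6·0.4 + 0.4·0.6)]² / 0.20² ≈ 97 per group, 194 in total.

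The plan states about 300 and gives no split between knowers and non-knowers. An 80:20 or 20:80 split needs exactly 300, so the claim of at least 80% power holds for any share of knowers from about 20% to 80%. For losses, 300/0.7 = 429, and 450 × 0.7 = 315, so 450 is enough. Nothing here needs correcting.

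**3. Effect if the exposure were built from H_HIVCT 23 with code 3 read as unknown (illustrative)**

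Let q be the share of knowers and m the share of knowers miscoded. Neither is in the Protocol. Assume also that miscoded women report use at the same 60% as other knowers. Use in the group coded as not knowing becomes

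p_u = [(1−q)·0.40 + q·m·0.60] / [(1−q) + q·m].

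Example, q = 0.5, m = 0.2, N = 300: (150·0.40 + 30·0.60)/180 = 43.3%. The difference falls from 20 to 16.7 points.

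Power, two-sided pooled-variance test, N = 300:

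| Share of knowers | none miscoded | 10% miscoded | 20% miscoded |
|---|---|---|---|
| 20% | 80.0% | 74.7% | 68.5% |
| 50% | 93.8% | 88.4% | 81.1% |
| 70% | 89.4% | 77.9% | 65.4% |
| 80% | 80.0% | 61.0% | 46.1% |

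If the exposure is H_HIVCT 22, the first column applies and the loss is zero.

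**4. The Section 4 heading against the rest of the Protocol**

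- Section 5.2 describes one exit interview for both cohorts. It covers the partner's testing history, whether a kit was offered, whether it was accepted, and why.
- Section 5.4 continues exit interviews until about 450 people in each cohort report acceptance and consent to follow-up.
- Section 7.3 analyses acceptance and its associated factors separately in each cohort.
- In Appendix 3, Section 3a, for clients in ART care, has four items: date of first positive test, ART start, whether status was disclosed, and to whom. That covers the disclosure factor of section 5.4, but not acceptance or the partner's history.
- PS 5 records the model through which a kit was offered. It does not record acceptance.

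**The case against.** The strongest reply is that Appendix 3 is a draft form. It states that response options, order and skip patterns may change once programmed, and codes and routing are exactly what such a caveat covers. This tempers both faults but removes neither, because nothing in the Protocol says that these two places will be corrected.

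On the code, a reader might infer that the ANC exposure is misclassified and the cohort underpowered. The documents do not support that. H_HIVCT 22 records knowledge of the result whether or not the woman reveals it, and no section derives the exposure from H_HIVCT 23. A miscoded woman could also be found, since Yes at H_HIVCT 20 (partner ever tested) and Yes at H_HIVCT 22 conflict with code 3 at H_HIVCT 23. The power losses need several conditions together, and their inputs q and m are assumptions.

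On the heading, a reader might infer that acceptance by HIV-positive clients is recorded nowhere. That is also too strong. The form's title says it is used at ANC or ART, and section 5.2 makes the intent clear. The ART secondary distribution register in Appendix 6 records acceptance, reasons for declining, and the partner's age, sex and education. What stands is narrower. The register has no field for the partner's testing history, and section 6.2 says no names or identifiers are entered for process data. No link from the register to a cohort participant is described.

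**Conclusion.** Both faults are real and both lie in the data collection form. The note to H_HIVCT 23 contradicts its own option list (3 against 4), so women coded by it carry a wrong partner status. How many is unknown, because the Protocol gives no share who would decline to say. Harm to the 60% versus 40% contrast is conditional. It arises only if the exposure is built from H_HIVCT 23 and the printed note survives programming, and it runs toward no difference if those women report use as other knowers do. With H_HIVCT 22 there is none.

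The Section 4 heading contradicts sections 5.2, 5.4 and 7.3. Followed as printed, the exit interview would lack individual-level acceptance and the H_HIVCT 11 to 23 partner items for HIV-positive clients. Relationship type, violence, decision-making and power items stand under other headings and are not affected. The gap matters most for people who decline the kit, who have no follow-up interview in which to recover the answers.

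This is a form correction to make before fielding. It is not a fault in the sample size or in the design.

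**What to change.** - In H_HIVCT 23, change the note so that a woman who knows but does not wish to share is coded 4.
- State in section 5.4 or 7.3 that H_HIVCT 22 defines the ANC exposure, and use H_HIVCT 23 codes 1, 2 and 4 as a consistency check on it.
- Re-head H_HIVCT 11 to 29 as asked of both cohorts, leaving H_HIVCT 1 to 10 for ANC women.
- In the same edit, check Use_HIVST 9 in the index follow-up questionnaire, where the note cites codes 99 and 98 but the list runs from 1 to 5.

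The cost is one edit of the electronic form, one sentence in the Protocol, and a few more interview minutes for HIV-positive clients. No extra visits are needed and no sample size figure changes.
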